4.3 Exclusion Criteria

Subjects will be considered ineligible to enter the study and receive vaccination if they meet any of the following exclusion criteria prior to receiving each vaccination.

- Presence of significant acute or chronic, uncontrolled medical or psychiatric illness (institution of new medical or surgical treatment, or a significant dose alteration for uncontrolled symptoms or drug toxicity within 3 months) as determined by medical history and/or physical exam.
- History of cancer.
- History of impaired immunoresponsiveness, including diabetes.
- Known hypersensitivity to a previous dose of influenza vaccine or allergy to eggs or any components of the study vaccines.
- Received influenza vaccination (TIV) during the 2008-2009 influenza season.
- Has known history of Guillain-Barré Syndrome
- History of systemic hypersensitivity reactions to egg proteins, or any other component of FLUVIRIN®, or life-threatening reactions to previous influenza vaccinations.
- Presently receiving or history of receiving any medications or treatments that affects the immune system such as allergy shots, immune globulin, interferon, immunomodulators, cytotoxic drugs or drugs known to be frequently associated with significant major organ toxicity, or systemic corticosteroids (oral or injectable) in the past 6 months. Inhaled and topical corticosteroids will be allowed.
- Participated in a clinical trial or received or planned administration of an investigational compound within 30 days before receiving study vaccine and/or during the study through the Day 28 evaluation.

- Was vaccinated with a registered vaccine within 14 days (for inactivated vaccines) or 28 days (for live vaccines) prior to receiving the study vaccine.
- History of anaphylactic type reaction to injected vaccines.
- History of drug or chemical abuse in the year before the study.
- Use of new prescription medications started within 7 days before study entry.
- Receipt of any blood products, including immunoglobulin, within 6 months before administration of study vaccine or anticipated receipt during the study period.
- Donation of blood or blood products within 8 weeks before study entry or at any time during the study.
- Has clinical signs of active infection and/or oral temperature of ≥ 38 °C (100.4 °F). Study entry may be deferred for such individuals at the discretion of the investigator.
- Has evidence or history of (within the previous 12 months) drug or alcohol abuse.
- Any condition that, in the opinion of the investigator, might interfere with study objectives.

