This first-in-human study was a phase I multicenter, double-blind, randomized, placebo-controlled trial to assess four vaccine doses, 0.3 µg, 1.0 µg, 3 µg and 10 µg compared to placebo. Vaccine/placebo was given intramuscularly (IM) at 0 and 28 days. Clinical and laboratory safety assessments took place 1 and 7 days after immunization. Immune response to M2e and flagellin was assessed by ELISA at 7, 14 and 28 days after each dose. Immune response to M2e was measured by ELISA. Seroconversion was defined as a serum IgG anti-M2e antibody (ug/ml) value \geq 0.0174 and a four-fold rise in titer.

The 0.3 and 1.0 µg doses were safe and well tolerated in all subjects and immunogenic in 18 (75%) of 24 vaccinees after the first dose and 23 (96%) after the second dose. In the 1.0 µg group, the geometric mean M2e antibody concentration was 0.4 µg/ml after the first dose and 1.7 µg/ml after the booster dose. Immune responses to flagellin were also robust and did not appear to negatively affect M2e antibody responses from the booster

dose. Higher doses (3 and 10 µg) showed a similar immunogenicity profile, but following the first dose, were associated with symptoms of cytokine release manifested by the presence of flu-like symptoms and elevated levels of C-reactive protein.

VAX102 was safe and able to induce high antibody levels to M2e at 0.3 and 1.0 µg doses. VAX102 is a promising new candidate M2e vaccine aimed to prevent or attenuate influenza A disease.

VAX102-02 summary

The results from VAX102-01 indicated that the vaccine (VAX102) was immunogenic at the lowest dose tested. VAX102-02 was designed to test doses of 0.03 and 0.1 µg by the IM and ID routes of administration (**Table 1**). This study was performed at a single site.

Dose (µg)	Route/Volume		No. of subjects
	IM 0.5	ID 0.1	
0.03	8	8	16
0.1	8	8	16
Total	16	16	32

VAX102 was well tolerated by both routes of administration. **Table 2** describes the symptoms after the first dose. The symptoms after the second dose were notably milder than the first dose (data not shown).

Table 2 includes the 16 subjects who received their dose by IM injection. However, the ID route of administration was also well tolerated. These studies indicated that all doses of 1 µg or below could be given safely.

Dose	Placebo n=16	0.03 µg n=8	0.1 µg n=8	0.3 µg N=6	1 µg n=18	3 µg n=6	10 µg n=14
Local ¹							
None	11 (69)	2 (25)	2 (25)	1 (17)	3 (17)	0	0
Mild	5 (31)	3 (37.5)	3 (37.5)	2 (33)	10 (56)	3 (50)	5 (36)

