Moderate	0	3 (37.5)	3 (37.5)	3 (50)	5 (28)	3 (50)	8 (57)
Severe	0	0	0	0	0	0	1 (7)
Systemic ²							
None	9 (56)	6 (75)	4 (50)	4 (67)	6 (33)	2 (33)	0
Mild	4 (25)	2 (25)	4 (50)	2 (33)	9 (50)	0	2 (14)
Moderate	2 (13)	0	0	0	3 (17)	4 (67)	6 (43)
Severe	1 (6)	0	0	0	0	0	6 (43)

[figure not shown]
¹ Local: injection site pain, redness, bruising or induration

² Systemic: headache, fatigue, joint pain, muscle aches, chills and sweats

The M2e immune response showed a dose related increase. **Figure 1** shows M2e antibody curve as defined by geometric mean concentrations measured at day 42 after two doses of VAX102 given on Days 0 and 28. At the highest doses (3 and 10 µg) the immune response plateaued at about 3 µg/ml. At a dose of 1.0 µg the antibody

concentration was 1.8 µg/ml. The right panel of **Figure 1** demonstrates that at Day 180 M2e antibody are still above the baseline.

Figure 1 . M2e antibody response after two doses of VAX102 at 0 and 28 days

VAX102-03 summary

VAX102-03 was designed to study the safety and immunogenicity of VAX102 given by different routes of administration (**Table 3**).

Route	IM	SC	ID	No. of subjects
Volume (ml)	0.5	0.5	0.1	
Dose (µg)				
0.3	8	8	8	24
1	8	8	8	24
2	8	8	0	16
Total	24	24	16	64

The study was performed at two clinical sites that had been involved in VAX102-01 and VAX102-02. In this study, we compared the safety and immunogenicity of VAX102 given by intramuscular (IM), subcutaneous (SC) and intradermal (ID) routes of administration. Healthy volunteers were randomized to receive 0.3 µg or 1.0 µg of VAX102 either IM, SC, or ID, or 2.0 µg of VAX102 IM or SC in an open label study.

Vaccine doses were administered at Days 0 and 28. There was an assessment of symptoms at each dose level before escalating the dose. C reactive protein (CRP) assays were performed on Day 0 and 1. Serum IgG anti-M2e antibody concentration (µg/ml) was assessed by ELISA on Day 42. VAX102 was administered to 64 subjects. VAX102 was well tolerated by all subjects in the 0.3 and 1.0 µg doses. After the first dose at 2 µg, 2 subjects in the 2 µg IM group had systemic symptoms compared to none in the SC group. The mean CRP level, range and fold increase were also significantly higher in the 2 µg IM group compared to the SC group. The differences in antibody titer between the IM and SC groups were not significant.

No. of subjects	Route	Dose (µg)	GM M2e	CRP (mean)	CRP (fold)
8	IM	0.3	0.5	0.8	1.8
8	IM	1	1.3	0.8	3.1
6	IM	2	2.3	1.4	5.9

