3 STUDY DESIGN

A multicenter, double-blind, randomized, placebo controlled vaccine study to assess the safety, reactogenicity and immunogenicity of one subject group receiving 1 µg VAX102 investigational vaccine with TIV, delivered intramuscularly into the nondominant arm as a prime vaccination, compared to placebo with TIV, in healthy normal adults of both genders. All subjects will receive TIV first followed by VAX102 or Placebo and undergo identical study procedures, as outlined in **Section 6**.

Eligible subjects will be assigned to a group according to a randomization code provided. The randomization is 1:1 for each of the 2 different groups and summarized as follows:

Table 6. Number of volunteers listed by dose and investigational vaccine			
Groups	Vaccine 1	Vaccine 2	Total # Subjects
A	TIV (std dose)	VAX102 1 µg	40
B	TIV (std dose)	Placebo	40
Total			80

The investigators will make a reasonable attempt to enroll an equal number of males and females into each of the groups of the study.

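### After 30 days, Section 4.3 leaves earlier recipients of VAX102 or another flagellin vaccine eligible for a study of a first VAX102 dose

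*Protocol*

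**What the plan says.** Protocol Section 3 describes VAX102 as "delivered intramuscularly into the nondominant arm as a prime vaccination", so a first exposure is what the trial means to study.

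Three criteria in Section 4.3 (repeated in the synopsis) could bear on earlier VAX102 exposure:

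- The investigational-product criterion: "Participated in a clinical trial or received or planned administration of an investigational compound within 30 days before receiving study vaccine". Its look-back is 30 days.
- The immune-treatment criterion: "Presently receiving or history of receiving any medications or treatments that affects the immune system such as allergy shots". The list that follows has a six-month limit on its natural reading and does not mention investigational vaccines.
- The closing criterion: "Any condition that, in the opinion of the investigator, might interfere with study objectives". This is left to each investigator.

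None of them names VAX102, flagellin or M2e. By contrast, anyone who has already had the 2008-2009 seasonal vaccine is excluded outright.

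The Introduction gives three facts about re-exposure. On tolerability in VAX102-02: "The symptoms after the second dose were notably milder than the first dose", with no figures. On immunogenicity of 1.0 µg in VAX102-01: "the geometric mean M2e antibody concentration was 0.4 µg/ml after the first dose and 1.7 µg/ml after the booster" dose. On persistence, it states that M2e antibody remained above baseline at Day 180 after two doses. The abbreviation list also shows a second STF2 (flagellin) product, VAX125.

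Section 9.2.9 scores each volunteer at the start as M2e positive or negative and reports responder proportions separately for the two strata.

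**The concern.** The protocol's own background says a second exposure differs from a first in both reactogenicity and antibody level. A volunteer from VAX102-01, -02 or -03 would contribute second-exposure (or later) data to a study meant to describe a first dose.

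Randomisation balances the number of such volunteers between groups in expectation. It does not balance what the new dose does to them, because only Group A receives VAX102. A prior recipient in Group A may react less and mount a booster response; one in Group B receives buffer and does neither. Group A's reactogenicity and its contrast with Group B would therefore tend to be understated. Safety, reactogenicity and tolerability form the primary objective, and the planned follow-on is the same combination in the elderly.

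Eligibility is fixed in the protocol, so an analysis plan cannot supply the missing criterion.

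**Working it through.** **Inputs from the protocol**

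- Group A size: 40 (Section 4.1).
- Geometric mean M2e at 1.0 µg: 0.4 µg/ml after the first dose, 1.7 µg/ml after the booster, doses 28 days apart (VAX102-01 summary).
- Responders at 0.3 and 1.0 µg: 18 of 24, then 23 of 24 (same summary). Check: 18/24 = 75% and 23/24 = 96%, as stated.
- First-dose systemic symptoms at 1 µg IM: none in 6 of 18, so any in 12 of 18 = 67% (Table 2, VAX102 without seasonal vaccine).
- People already given VAX102: 6 + 18 + 6 + 14 = 44 in VAX102-01 (Table 2), 32 in VAX102-02 (Table 1) and 64 in VAX102-03 (Table 3). Total 44 + 32 + 64 = 140.

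**Not in the protocol:** the number of prior recipients who would enrol, and the response to re-exposure after more than 30 days. The number re-exposed in Group A, k, is therefore an assumption, shown at 2, 4 and 8. With 1:1 allocation these imply about 4, 8 and 16 prior recipients among the 80 enrolled.

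**1. Post-dose M2e level.** Booster-to-prime ratio = 1.7/0.4 = 4.25. If every re-exposed subject responded like a booster recipient, the Group A geometric mean would be multiplied by 4.25^(k/40).

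| k of 40 | Multiplier | Inflation |
|---|---|---|
| 2 | 4.25^0.05 = 1.075 | about 8% |
| 4 | 4.25^0.10 = 1.156 | about 16% |
| 8 | 4.25^0.20 = 1.336 | about 34% |

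**2. Change from baseline.** Section 9.2.9 tests the change in log titre, not the post-dose level alone. Let b0 be a naive subject's baseline and b a prior recipient's. The re-exposed fold-rise, 1.7/b, is smaller than the naive fold-rise, 0.4/b0, whenever b/b0 exceeds 4.25. A four-fold rise to 1.7 is missed when b exceeds 1.7/4 = 0.425 µg/ml. The text gives no Day 180 concentration from which to judge b. The same re-exposed subjects can thus raise the post-dose geometric mean and lower the fold-rise.

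**3. Reactogenicity.** Extreme case: re-exposed subjects have no systemic reaction at all. The Group A rate is then (12/18) × (1 − k/40).

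| k of 40 | Any systemic reaction |
|---|---|
| 0 | 66.7% |
| 2 | 63.3% |
| 4 | 60.0% |
| 8 | 53.3% |

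If re-exposure only halved the risk, the k = 4 figure would be 0.667 × (1 − 0.05) = 63.3%. For scale, the 95% half-width of a 67% rate in 40 subjects is about 1.96 × √(0.667 × 0.333/40) = 15 percentage points. The k = 4 shift of 3 to 7 points lies within that, but it is systematic and towards better tolerability.

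**4. After the fix,** k = 0: the multiplier is 1.00 and the reaction rate is unshifted.

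**The case against.** The case on the other side is substantial.

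- **Nothing shows it will happen.** A reader might infer that the trial returns to the earlier sites, because of VAX102-03 the Introduction says: "The study was performed at two clinical sites that had been involved in VAX102-01 and VAX102-02". That concerns VAX102-03. The protocol does not say who the two VAX102-07 centres are, or that any earlier volunteer will enrol. The 140 is the pool, not a forecast. The k = 8 case needs about 16 of them, 11% of the pool, to return. This stands.
- **The 4.25 ratio does not describe the people left eligible.** It comes from a 28-day interval, which the 30-day rule already excludes, and from 1.0 µg given IM; the pool includes other doses and SC and ID routes. This stands, so the M2e inflation figures are illustrative.
- **Bias confined to Group A is too strong a reading.** Prior recipients would fall in both groups, and persisting antibody could raise baseline level, later level and the proportion with a titre in Group B too. Only the effect of the new dose is confined to Group A.
- **An overstated M2e response is not established for every endpoint.** Step 2 shows that change from baseline could move the other way.
- **Safeguards exist.** Day 0 M2e and flagellin antibody could help identify prior recipients. The serostatus split partly protects the responder proportions. An investigator could invoke the immune-treatment or closing criterion. But no such split is stated for reactogenicity, geometric means, t-tests or ANOVA, and the two criteria depend on each site's reading.
- **The evidence for milder symptoms is thin.** It is a statement without figures from a study of 0.03 and 0.1 µg. This limits the size claimed, not the direction.

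**Conclusion.** The gap is real: a study of a prime dose admits people who are not naive to the product, with no stated means of identifying them. If any enrol, the re-exposure effect would act only in Group A, randomisation would not remove it, and it would tend to understate first-dose reactogenicity. For M2e, the post-dose level would probably be higher and the fold-rise possibly lower.

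The size cannot be fixed from the documents. With 2 to 8 of 40 re-exposed, the calculations give 8% to 34% on the M2e geometric mean and a fall in any-systemic reactions from 67% to between 63% and 53%. They rest on assumed numbers re-exposed, a 28-day booster response carried over to longer intervals, and complete absence of systemic reactions on re-exposure, so they mark the upper end. The documents do not support saying that the trial is biased, that only Group A's data would be touched, or that M2e would be inflated four-fold. This is a cheap improvement worth making, not a flaw that invalidates the design.

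**What to change.** Add to Section 4.3 and to the synopsis an exclusion for receipt, at any time, of VAX102 or any other flagellin- or M2e-containing investigational vaccine. Add a matching question to the screening history in Section 6.1. This treats the investigational antigen as the protocol already treats same-season influenza vaccine.

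If prior recipients have already been enrolled, record the product and date for each. Show reactogenicity and M2e results with and without them; the safety population itself need not change.

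The cost is one criterion, one screening question and a small loss of experienced volunteers at the sites.

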4.4 Subject Enrollment and Randomization

Eligible subjects will be assigned to a group according to a randomization code provided by an independent statistician. The independent statistician will provide the randomization information to the investigational pharmacist or designee. Within each dose group, subjects will be randomly assigned to treatment as described previously in **Table 6**.

On Study Day 0, the investigational pharmacist or designee will be provided with each eligible and consenting initials, subject ID number (SID), age and gender by the study site's personnel. The investigational pharmacist or designee will use the randomization list provided by the independent statistician to assign the next available randomization code and determine treatment assignment. For each subject randomized, the pharmacist will prepare a duplicate label bearing the subject's SID number, subject's initials, and date and affix the label to a syringe. The randomization code will be transcribed onto the Investigational Product Accountability Log along with the SID number. The investigational pharmacist or designee will then prepare the appropriate test article for each subject.

Investigational vaccine will be prepared by an unblinded investigational pharmacist who will not be involved in vaccine administration or subsequent clinical assessments.

The study design incorporates ongoing review of the safety and reactogenicity of the vaccine on Day 7 after vaccination.

Sponsor personnel involved in generation and recording of immunogenicity assays will be unblinded only after all assays and repeats are complete and final data sets are provided to data management personnel and locked in the database.

4.5 Unblinding

This is a phase II, double-blinded, randomized, placebo-controlled study to investigate the safety and immunogenicity of TIV plus one VAX102 dose (1.0 µg) versus TIV plus placebo. In order to allow unbiased accrual, the randomization list will be withheld from all sponsor personnel until the final subjects' data at the end of the Day 28 (± 2) assessments have been entered, after resolution of all data queries, after all immunogenicity samples have taken through Day 28 (± 2), and after the safety database has been locked.

Treatment assignments will be provided:

- to sponsor personnel not involved in the performance of immunogenicity assays 28 days after the investigational vaccine dose (and completion of safety data) as above,
- to clinical site personnel only after all case report forms are verified, all queries are resolved, and the entire safety database locked,
- to sponsor personnel involved in the generation and recording of immunogenicity data only after all assays and repeats are complete and final datasets are provided to data management personnel and locked in the database.

4.6 Withdrawal of Subjects from the Study

Every reasonable effort should be made to ensure that each subject complies with the protocol and completes all study visits. However, a subject may withdraw - or be withdrawn involuntarily - from participation if:

- The subject withdraws consent.
- The investigator recommends discontinuation in the interest of the subject's safety (i.e., adverse event related) or because of significant and irremediable protocol non-compliance.
- The subject becomes pregnant as evidenced by a positive pregnancy test.
- VaxInnate, the IRB, or the FDA terminates the clinical trial for safety or other reasons.

Subjects may be withdrawn from treatment and, if consenting, continue to complete a per-protocol safety evaluation. Where this is deemed impractical (e.g., a chronically non-compliant subject) or where the subject does not consent to further follow-up, a complete Day 28 (± 2) (**Section 6.2.4**) and study closeout visit case report form(s) will be completed on any subject prematurely withdrawn from the clinical trial on the day of withdrawal. Any adverse event leading to early discontinuation will be followed to resolution. Any woman who becomes pregnant during the trial will be followed until delivery, and the outcome of the pregnancy documented. No subject prematurely withdrawing/withdrawn will be replaced.

4.7 Halting Rules

- If one or more subjects experience a clinically significant AE or laboratory abnormality (Grade 3 or 4), there will be no further enrollment until a full safety review is performed.
- The study will be halted (no new enrollments and no further investigational product administered) if one of the following occurs:
 - a. One subject experiences a serious adverse event (SAE) assessed as possible, probably or definitely related to investigational product or
 - b. There is a subject death assessed as possibly, probably or definitely related to investigational product.

A safety monitoring committee (SMC) comprised of a Principal Investigator from each site, VaxInnate, and an Independent Safety Monitor, will be set-up to assess in a blinded fashion the safety and reactogenicity should one of the above halting rules be met. The Independent Safety Monitor may be unblinded to study treatment, as needed, to adequately assess safety issues.

5 STUDY PRODUCT DESCRIPTION

5.1 Investigational Product

5.1.1 VAX102 (STF2.4xM2e[Hu**])**

The VAX102 will be supplied in individual 3 mL glass vials containing 0.75 mL of vaccine at a concentration of 20 µg of STF2.4xM2e(Hu) per 1 mL. The STF2.4xM2e(Hu) vaccine is formulated in a Phase I formulation buffer (F105) that contains 10 mM Tris, 10 mM Histidine, 5% (w/v) sucrose, 75 mM NaCl, 0.1 mM EDTA, 0.5% (v/v) ethanol and 0.02% (w/v) polysorbate-80 at pH 7.2.

The study design incorporates one dose level 1 µg. This 1 µg dose level will be prepared by a field mix procedure where a specific amount of vaccine is combined with a specified volume of VAX102 vaccine diluent (F105). The investigational pharmacist or trained study personnel compounding the individual subject dosages will follow a dose specific procedure to ensure the proper final dosage strength is achieved. This compounding step will be performed on the day of administration (Day 0); the individual vials for the each subject will be provided along with the compounding procedure.

5.1.2 Trivalent Inactivated Influenza Vaccine (TIV)

FLUVIRIN® (Novartis) Expiration date: 30 June 2009

Each 0.5-mL dose contains a total of 45 µg of influenza virus hemagglutinin (HA) from each of the following 3 strains: A/Brisbane/59/2007(H1N1); A/Uruguay/716/2007 (H3N2), an A/Brisbane/10/2007-like strain; and B/Florida/4/2006.

5.1.3 Placebo (F105 – Formulation Buffer)

F105 buffer contains 10 mM Tris, 10 mM Histidine, 5% (w/v) sucrose, 75 mM NaCl, 0.1 mM EDTA, 0.5% (v/v) ethanol and 0.02% (w/v) polysorbate-80 at pH 7.2. It is the buffer that is used to formulate VAX102.

